6.7.2. Per-Protocol Random Subcohort for Immunogenicity

The Per-Protocol Random Subcohort for Immunogenicity (PPRSI) will be used as the analysis population to characterize immunogenicity of mRNA-1273. The Per-Protocol Subcohort for immunogenicity consists of participants in the FAS who are sampled into the Random Subcohort and

- a). received both planned doses (i.e. received the treatment as the participant was randomized to) with dose 2 received within [21, 42] days after dose 1, and
- b). no major protocol deviation that impact critical or key data.

A subset of the planned Random Subcohort that is representative of the Random Subcohort may be used to expedite analyses to characterize immunogenicity of mRNA-1273.

6.7.3. Immunogenicity Data

The following immunogenicity assessments (assays) may be used in this study:

- Serum bAb level against SARS-CoV-2 as measured by enzyme-linked immunosorbent assay (ELISA) specific to the SARS-CoV-2 S protein (vaccine antigen), tests may include VAC65 Spike IgG Antibody.
- The MSD-ECL Multiplex Assay (MSD-ECL = meso scale discovery – electrochemiluminescence assay) measures binding antibody to antigens corresponding to: Spike; the Receptor Binding Domain (RBD) of the Spike protein; and Nucleocapsid protein (NP), which is not contained in mRNA-1273.

- Pseudovirus nAb assay for measuring neutralizing antibodies against SARS-CoV-2 Spike-pseudotyped viruses: Pseudovirus neutralizing antibody ID50 and ID80 titers (PsVNT50 and PsVNT80)
- Wild Type Live virus-nAb assays measuring antibody-mediated neutralization of live wild-type SARS-CoV-2 (Wild Type Live virus-nAb MN [microneutralization] 50 titers)

6.7.4. Summary of Antibody-Mediated Immunogenicity Endpoints

Data from quantitative immunogenicity assays will be summarized for each treatment group using positive response rates and geometric means with 95% CI at each timepoint when an assessment is performed. Data from qualitative (i.e., yielding a positive or negative result) assays will be summarized by tabulating the frequency of positive responses for each assay by treatment group and by baseline status based on bAb specific to SARS-CoV-2 NP as measured by *Roche Elecsys* SARS-CoV-2 assay, if applicable, at each timepoint that an assessment is performed.

At the time of the final blinded efficacy analysis, immunogenicity analysis to characterize immunogenicity of mRNA-1273 may be performed. At the time of immunogenicity analysis, data for bAb to Spike (MSD, PPD-VAC65), RBD (MSD); and Pseudovirus neutralizing antibody ID50 and ID80 titers are expected. The assay by MSD to measure bAb against RBD may not have been validated yet at the time of the immunogenicity analysis, in that situation, bAb against RBD by MSD will not be summarized/analyzed. Immunogenicity data at the pre-specified timepoints: baseline (Day 1), Day 29 and Day 57 will be included.

- Geometric mean titer (GMT) or value with corresponding 95% CI will be provided at each time point. The 95% CIs will be calculated based on the t-distribution of the log-transformed values then back transformed to the original scale for presentation. GM level and corresponding 95% CI will be plotted at each timepoint. The

following descriptive statistics will be also provided at each time point: the number of subjects (n), median, minimum and maximum.

- Geometric mean fold rise (GMFR) with corresponding 95% CI will be provided at each post-baseline timepoint over pre-injection baseline at Day 1. The 95% CIs will be calculated based on the t-distribution of the log-transformed values then back transformed to the original scale for presentation. GMFR and corresponding 95% CI will be plotted at each timepoint. The following descriptive statistics will be also provided at each time point: the number of subjects (n), median, minimum and maximum.
- Reverse cumulative distribution function curve (RCDF) at each time point. The number and percentage of subjects with fold-rise ≥ 2 , fold-rise ≥ 3 , and fold-rise ≥ 4 from Baseline at each post injection time points will be tabulated with 2-sided 95% Clopper Pearson CIs. If assay-specific fold rise criteria are available, the number and percentage of subjects with fold-rise exceeding the criteria with 95% CI will be provided instead.
- Proportion of subjects with seroconversion due to vaccination will be tabulated with 2-sided 95% Clopper-Pearson CIs at each post-baseline timepoint. Seroconversion due to vaccination at a subject level may be defined as a change from below the LLOQ to equal to or above LLOQ, or 4-fold rise if baseline is equal to or above LLOQ. The definition of seroconversion may depend on assay-specific performance characteristics and the final definition of seroconversion due to vaccination will be documented in a memo.

The GMT and GM levels will be calculated using the following formula:

$$10^{\left\{ \frac{\sum_{i=1}^n \log_{10}(t_i)}{n} \right\}}$$

where t_1, t_2, \dots, t_n are n observed immunogenicity titers or levels.

The geometric mean fold rise (GMFR) measures the changes in immunogenicity titers within subjects. The GMFR will be calculated using the following formula:

$$10^{\left\{ \frac{\sum_{i=1}^n \log_{10} \left(\frac{v_{ij}}{v_{ik}} \right)}{n} \right\}} = 10^{\left\{ \frac{\sum_{i=1}^n \log_{10}(v_{ij}) - \log_{10}(v_{ik})}{n} \right\}}$$

where, for n subjects, v_{ij} and v_{ik} are observed immunogenicity titers or levels for subject i at time points j and $k, j \neq k$.

6.7.5. Analysis of Antibody-Mediated Immunogenicity Endpoints

To assess the magnitudes of the differences between the two treatment groups (mRNA-1273 vs. Placebo) in SARS-CoV-2-specific nAb and S protein-specific bAb, a mixed model for repeated measures (MMRM) using SAS PROC MIXED will be used.

For each of the SARS-CoV-2-specific nAb and S protein-specific bAb, the analysis will be performed separately for subjects who are seropositive and seronegative (as measured by Roche Elecsys SARS-CoV-2 assay) at baseline respectively. The model will include all available log-transformed antibody titers at each post-baseline visit as the dependent variable, treatment groups, visit (as a class variable), and treatment-by-visit interaction visit as fixed effects, with adjustment for stratification factor used for randomization, baseline log-transformed anti-body titers if applicable, and subject as a random effect. The model may also adjust for minority group used to sample for the random subcohort. An unstructured covariance structure will be used to model the within-subject errors. A Kenward-Roger approximation will be used for the denominator degrees of freedom. If there is a convergence issue due to the unstructured covariance matrix, a compound symmetry covariance structure will be used to model the within-subject errors. No imputation of missing data will be done.

The geometric least squares mean (GLSM) and corresponding 2-sided 95% CI for the antibody titers for each treatment group will be provided by visit. The GLSM, and corresponding 95% CI results in log-transformed scale estimated from the model will be

back-transformed to obtain these estimates in the original scale. Geometric mean ratio (GMR), estimated by the ratio of GLSM and the corresponding 2-sided 95% CI will be provided to assess the treatment difference between mRNA-1273 group vs. placebo group at each visit. With each treatment group, within-group comparison of timepoints may also be estimated using the same model.

In addition, an analysis of covariance (ANCOVA) model with the treatment group as explanatory variables, adjusting for the stratification factor at randomization, baseline value if applicable, will be used to assess the treatment effect at specific timepoints (scheduled visits) such as Day 57. GLSM with 95% CI for each treatment group, GMR with 95% CI for treatment difference will be estimated from the ANCOVA model. The model may also adjust for minority group used to sample for the random subcohort.

6.7.6. Summary of Immunogenicity in COVID-19 Cases on mRNA-1273 with negative SARS-CoV-2 status at baseline

To characterize immunogenicity of mRNA-1273, immunogenicity data (Section 6.7.3) will be analyzed using the Per-Protocol Random Subcohort for Immunogenicity.

It is of interest to examine the immune response in subjects on mRNA-1273 with baseline SARS-CoV-2 negative status who were COVID-19 or SARS-CoV-2 infection cases. Summary of immunogenicity may be provided in a subset of baseline SARS-CoV-2 negative participants on mRNA-1273 who were COVID-19 cases based on adjudication committee assessments.

6.8. Exploratory Analysis of Efficacy

Exploratory analyses of efficacy described in this section will not be performed at the interim analyses, and may be performed at the primary analysis, with the exception of exploratory analyses of Burden of Disease (BOD) and Burden of Infection (BOI) that will be performed at the interim analyses and provided to the DSMB.

6.8.1. Vaccine Efficacy Against Burden of Disease

Exploratory analysis of BOD due to COVID-19 will be performed. A BOD score is defined based on the post SARS-CoV-2 infection follow-up to reflect the worst severity of symptoms as shown in the table below.

Table 7: Burden of Disease Score

Subject State (Worst Category Following Disease Detection)	BOD Score
Without COVID-19 (uninfected/asymptomatic infection)	0
COVID-19 without hospitalization (symptomatic without hospitalization)	1
COVID-19 with hospitalization	2
Death	3

Summary of BOD score, number and percentage of subject with each level of BOD score, will be provided by treatment group using the PP Set. A t-test of the BOD scores may be performed to compare mRNA-1273 vs. placebo group.

To assess impact of baseline risk of severe disease on the vaccine effect regarding disease severity, summary of BOD may be provided by randomization strata (i.e. ≥ 65 years, < 65 years at risk, and < 65 years not at risk).

In order to assess the disease burden in subjects with COVID-19, the above analyses may also be performed in participants with COVID-19, i.e. subjects with BOD score of zero will be excluded from the analysis.

While transparent, the proportions in the summary table will change with increased follow-up time as more subjects inevitably acquire disease. This makes comparisons across

different periods of follow-up difficult. To augment this analysis, a proportional means model will be used to assess the treatment effect on BOD between mRNA-1273 and placebo in terms of ratio of mean severity score. The proportional means model allows for direct comparisons across different periods of follow-up, unaffected by differential follow-up. A proportional means model including vaccination group as fixed effect and stratified with stratification factor at randomization will be used to assess the vaccine effect on BOD. The VE for the BOD score will be estimated as 1 minus the ratio of means as estimated by the proportional means model and reported with 95% confidence intervals.

6.8.2. Vaccine Efficacy Against Burden of Infection

To fully understand the impact of vaccination on disease severity, asymptomatic infections should also be evaluated. Similarly, a burden of infection (BOI) score will be calculated as in the table below and used to understand the impact. Because asymptomatic infection is identified by seroconversion only at scheduled visits at which samples for RT-PCR test and/or serum samples will be taken (e.g. months 1, 2, 7, 13 and 25), summary of BOI will be provided for relevant periods (e.g. Baseline through M1, M1 through M2, M2 through M7, M7 through M13, and M13 through M25) only using subjects who have serological data for that period. With protocol amendment 6, at the unblinding/participant decision visit/Open-label-Day 1 (OL-D1) visit, NP swab for RT-PCR tests and serum samples will be taken. The relevant periods will be updated to Baseline through M1, M1 through M2, M2 through M7/OL-D1 whichever is earlier.

A t-test of the BOI scores may be performed to compare mRNA-1273 vs. placebo group. A proportional means model including vaccination group as fixed effect and stratified with stratification factor at randomization will be used to assess the vaccine effect on BOI. The VE for BOI will be estimated as 1 minus the ratio of mean BOI scores and reported with 95% confidence intervals.

Table 8: Burden of Infection Score

Patient State (Worst Category Following Disease Detection)	BOI Score
No infection	0
Asymptomatic infection	1/2
COVID-19 without hospitalization (Symptomatic without hospitalization)	1
COVID-19 with Hospitalization	2
Death	3

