- Clinical signs indicative of severe systemic illness, Respiratory Rates ≥ 30 per minute, Heart Rate ≥ 125 beats per minute, SpO₂ $\leq 93\%$ on room air at sea level or PaO₂/FIO₂ < 300 mm Hg, OR
- Respiratory failure or Acute Respiratory Distress Syndrome (ARDS), (defined as needing high-flow oxygen, non-invasive or mechanical ventilation, or ECMO), evidence of shock (systolic blood pressure < 90 mmHg, diastolic BP < 60 mmHg or requiring vasopressors), OR
- Significant acute renal, hepatic or neurologic dysfunction, OR
- Admission to an intensive care unit or death.

From Medically-Attended HCP Visit (site or external)

- Positive virologic result by RT-PCR for SARS-CoV-2 infection

PCR results on NP Swab, Nasal Swab, or Saliva Sample

During the course of the study, participants with symptoms of COVID-19 will be asked to return within 72 hours or as soon as possible to the study site or medically qualified staff from the study site will conduct a home visit as soon as possible to collect an NP swab sample (for RT-PCR), collect a blood sample for immunologic analysis of SARS-CoV-2 infection, and to evaluate for COVID-19. Both study site visits and home visits are referred to as Illness Visits. An additional NP swab sample will be collected and tested for the presence of other respiratory pathogens.

In addition, the study site may collect an additional (non-study/local) respiratory sample for SARS-CoV-2 testing to be able to render appropriate medical care for the study participant as determined by local standards of care. If neither a study site visit or home visit is possible,

participants will be sent a saliva kit via courier or other Sponsor-approved method. The study site will arrange to retrieve a saliva sample by local courier or other Sponsor-approved method, and the sample will be tested by RT-PCR for SARS-CoV-2. If participants are confirmed to have SARS-CoV-2 infection, the investigator will notify the participant, and the participant's primary care physician, of the diagnosis. If the study participant does not have a primary care physician, the investigator will assist them to obtain one. The participant will also be instructed on infection prevention measures consistent with local public health guidance.

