If scheduled, a study site Illness Visit includes assessments such as medical history, physical examination, blood sampling for clinical laboratory testing, and 2 NP swabs, 1 for viral polymerase chain reaction (PCR) SARS-CoV-2 testing and 1 for multiplex PCR testing for respiratory viruses, to evaluate the severity of the clinical case. Radiologic imaging studies may be conducted. Blood samples will be collected for potential future immunologic assessment of SARS-CoV-2 infection. Every effort to complete an Illness Visit that includes both the NP swabs and blood draw should be made by the site, even in the presence of a local positive or negative Clinical Laboratory Improvement Amendments (CLIA) certified or CLIA-certified waiver laboratory result for the participant.

Cases are defined as participants meeting clinical criteria based both on symptoms for COVID-19 and on RT-PCR detection of SARS-CoV-2 from samples collected within 72 hours of the study participant reporting symptoms meeting the definition of COVID-19. Participants who are hospitalized for COVID-19 without the opportunity for a clinic or home visit will also be considered cases, assuming that the symptomatology criteria for COVID-19 are met and a respiratory sample is positive for SARS-CoV-2 by PCR at a CLIA-certified or CLIA-certified waiver laboratory. Investigators are encouraged to try to obtain a respiratory sample during the course of hospitalization for submission to the study central laboratory, if feasible. The investigator should determine if the criteria for severe COVID-19 has been met.

Evidence of severe COVID-19 is defined as in [Section 8.1.1](#).

All clinical findings will be recorded in the eCRF. All confirmed cases of COVID-19 will be captured as MAAEs, along with relevant concomitant medications and details about severity, seriousness, and outcome.

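### The Burden of Infection summary requires period serology from everyone, including participants whose score of 1, 2 or 3 is already known without it

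*SAP*

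**What the plan says.** SAP Part A section 6.8.2 gives the reason for the rule: "asymptomatic infection is identified by seroconversion only at scheduled visits". It therefore summarises BOI by period, "only using subjects who have serological data for that period". Following Protocol Amendment 6, the last Part A period is "M2 through M7/OL-D1 whichever is earlier".

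Table 8 in that section scores the "Worst Category Following Disease Detection": no infection 0, asymptomatic infection 1/2, COVID-19 without hospitalisation 1, with hospitalisation 2, death 3. No sentence exempts a participant whose state is already documented. The section then plans a possible t-test and "A proportional means model including vaccination group as fixed effect", with no analysis set stated for either and without repeating the serology restriction.

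Section 6.8 makes BOI exploratory but names it among the "exploratory analyses of Burden of Disease (BOD) and Burden of Infection (BOI) that will be performed at the interim analyses and provided to the DSMB".

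**The concern.** The restriction is wider than its reason. A missed blood sample leaves 0 and 1/2 indistinguishable, but it does not obscure a documented COVID-19 case, a hospitalisation or a death. Requiring it from everyone makes inclusion depend on being alive and attending after the event, on a scale whose top level is death.

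Attendance may also differ by arm. Protocol section 6.2.8.2 allowed unblinding of participants seeking vaccination outside the study, accepted a verbal interview as the final safety assessment, and withdrew those found to be on placebo who intended to be vaccinated elsewhere. A placebo case already scoring 1 or 2 could lose that score for lack of a later sample. At stake is the accuracy of an exploratory severity measure that was also planned for the DSMB.

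**Working it through.** The plan states no BOI figure, so there is none to reproduce. The check is a reading of the rule, followed by two illustrations of size.

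**1. Which sample qualifies.** Section 6.8.2 ends each period at a scheduled sampling visit. Section 6.3.2.1.3 defines seroconversion at scheduled post-baseline visits, and section 6.3.1.1 lists nucleocapsid testing at months 1, 2, 7, 13 and 25. The natural reading is the closing scheduled sample, which someone who dies before the visit cannot give. This remains an inference, because the term is undefined.

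**2. Other serum in the period.** Protocol section 8.1.2 has staff "collect a blood sample for immunologic analysis of SARS-CoV-2 infection" at the Illness Visit, and SAP Part A Table 10 maps Illness Visit Day 1 as an immunogenicity visit. Some participants who later die may therefore have serum. However, the same protocol section describes the blood as being for possible later assessment, and adds: "Participants who are hospitalized for COVID-19 without the opportunity for a clinic or home visit will also be considered cases". Those cases may have none.

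**3. Sister analyses.** Burden of Disease (section 6.8.1) uses the PP Set with no serology condition. All-cause mortality (section 6.8.4) includes every death from randomisation.

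**4. Share of placebo burden lost.**
- Burden = 1 × mild + 2 × hospitalised + 3 × deaths + 0.5 × asymptomatic.
- Placebo cases: 196 adjudicated cases (SAP Part A section 6.4.2.2) and VE 94.5% (SAP Part B and Part C, Introduction) give about 196 / 1.055 = 185.8; 185 is used.
- Assumptions not in the documents: 10% hospitalised (18.5), 50 to 200 asymptomatic infections, deaths 1%, 2% or 4% of cases.
- Example, 2% deaths and 50 asymptomatic: 162.8 + 37 + 11.1 + 25 = 235.9; lost 11.1 / 235.9 = 4.7%.
- Deaths alone: 1.8% to 2.4%, 3.6% to 4.7% and 7.0% to 9.1% for the three fatality levels.
- If a quarter of hospitalised cases also lack the sample (2 × 0.25 × 18.5 = 9.25): from (5.55 + 9.25) / 307.2 = 4.8% to (22.2 + 9.25) / 243.3 = 12.9%.

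**5. What that does to VE.** If shares s_P and s_V of burden are lost on placebo and vaccine, and the few people dropped from the denominators are ignored, VE after loss = 1 − (1 − VE) × (1 − s_V) / (1 − s_P). Equal shares leave VE unchanged. Loss on placebo only lowers it by (1 − VE) × s_P / (1 − s_P):
- VE 94%, s_P 2%: 0.06 × 0.02 / 0.98 = 0.1 point.
- VE 94%, s_P 13%: 0.06 × 0.13 / 0.87 = 0.9 point.
- VE 80% (assumed), s_P 13%: 0.20 × 0.13 / 0.87 = 3.0 points.

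**6. Scenarios at the design rates.** Protocol section 9.3 gives 15,000 × 0.85 = 12,750 per arm and 6-month incidence of 0.75% versus 0.30%, so 95.6 and 38.25 cases. Assumed: 5% hospitalised, asymptomatic infections 0.5 to 1 times the cases.

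| Deaths as share of cases, placebo / vaccine | VE, deaths kept | VE, deaths dropped |
|---|---|---|
| 1% / 1% or 5% / 5% | 60.0% | 60.0% |
| 2% / 0% | 61.0–61.2% | 59.4–59.5% |
| 5% / 0% | 62.4–62.9% | 58.4–58.7% |
| 2% / 5% | 58.2–58.5% | 60.8–60.9% |

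The largest gap is 62.9 − 58.4 = 4.5 points, and the last row moves the other way.

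**The case against.** A reader might infer that every death in a period is lost by construction, and that VE is therefore biased toward zero. The documents support neither step. The qualifying sample is undefined and Illness Visit serum exists. The score is the worst category after detection, so someone sampled at a period's close who dies later could still score 3. Having more disease on placebo does not by itself give bias toward zero; that needs a larger share of burden lost on placebo than on vaccine. The restriction is attached to the summary, and it is unstated whether it governs the model that yields VE.

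The DSMB argument is also limited. SAP Part A section 6.5 says data for the infection endpoint, which uses nucleocapsid seroconversion, were unavailable at the first interim and primary analyses. Section 6.9.2.1 bases harm monitoring on COVID-19 and severe COVID-19 counts, not BOI. Severe disease and COVID-19 death have their own secondary endpoints.

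These points stand and limit the consequence. They do not justify requiring serology from participants whose score is known, and the undefined term and unstated analysis set are gaps in their own right.

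One further objection concerns the remedy. Keeping all cases, but other participants only when they have serology, makes inclusion depend on outcome and over-represents symptomatic disease relative to asymptomatic infection. That is correct, and the fix must deal with it in the main analysis.

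**Conclusion.** The rule as written is flawed but of minor consequence. It asks for serology where serology adds nothing to the score. On the closing-sample reading it excludes participants who die in the period, and hospitalised or withdrawn cases who miss the visit. The effect on VE against BOI is nil when both arms lose the same share of burden, about 0.1 to 0.9 point for a 2% to 13% loss on placebo only at VE 94%, and up to about 4.5 points, in either direction, across the scenarios tried. Those sizes rest on assumed hospitalisation, fatality and asymptomatic rates, on VE against BOI being close to VE against COVID-19 where 94% is used, and on the restriction carrying through to the VE estimate. The primary and secondary efficacy conclusions are not affected.

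**What to change.** For BOI, state that:

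- participants with documented COVID-19, COVID-19 hospitalisation or death take 1, 2 or 3 from Table 8 whatever their serology;
- period serology means the closing scheduled sample and is required only to assign 0 versus 1/2;
- in the main BOI analysis, participants without documented COVID-19 or death who lack that sample are handled by weighting or imputation within arm and randomisation stratum, so that cases are not over-represented;
- the same analysis set applies to the summary, the t-test and the proportional means model.

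Report by arm how many cases, hospitalisations and deaths the rule in section 6.8.2 excluded. If none were, that settles the matter.

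SAP Part B and Part C section 3.4 lists BOI among the Part A exploratory endpoints already evaluated, with results in the final blinded-phase report or in articles. This should therefore be presented as a labelled sensitivity re-analysis. The cost is a short text change, some extra programming, and an assumption that serology is missing at random within arm and stratum.
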